#### **Determination of the maximum tolerated dose (MTD)**

An adaptive dose escalation design will be used to determine the MTD in study Part 1 (all

.

<sup>33 Part 3 was added by Amendment 7, see section 15.6.2.6

17 Oct 2018 Version 8.0 Page: 41 of 395

comer). The MTD is defined as the highest dose that can be given such that not more than 20% of subjects experience a DLT during Cycle 1.

Without the occurrence of toxicities, dose escalation could be stopped and RP2D may be determined based on PK and/or PD results. The decision to continue treatment for an individual subjects will be made by the investigator according to the criteria specified in the protocol (Section 8.4).

Each cohort will be evaluated after all subjects have completed the first 21 days of treatment (which will subsequently referred to as "Cycle 1") or early discontinued.

[figure not shown]
Safety monitoring will occur by telephone conferences with participation of the investigators and the sponsor on a regular basis.

At the time of dose escalation the available clinical safety information is discussed in a telephone conference by the involved investigators and representatives from the Sponsor including the Study Medical Expert as well as representatives of other clinical and if required further contributing functions (drug safety monitoring team – DSMT). During this telephone conference it will be judged if dose escalation can proceed as planned according to the procedure outlined below. Dose escalation for subsequent cohorts will only be considered after full evaluation of at least Cycle 1 safety data from the previous cohort.

The National Cancer Institute (NCI) Common Terminology Criteria for Adverse Events Version 4.03 (CTCAE v4.03) will be used to grade toxicities / adverse events. In general, the assessment of relationship between adverse events (AEs) and BAY 1163877 will be performed as described in Section 9.5.1.2.3.

The dose escalation will be performed as follows:

- Initially 3 subjects per dose level will be enrolled. In case 2 or more sites are conducting the dose escalation part, the initial enrolment of 4 subjects per dose level is optional.
- The starting dose of BAY 1163877 is 50 mg given as a single dose on Cycle 1, Day 1, and twice daily (b.i.d.) from Cycle 1, Day 3 (100 mg / day).
- The maximum dose escalation will be 2-fold.
- Possible daily doses of BAY 1163877 starting from 100mg in increments of 100mg.
- The possible maximum dose of BAY 1163877 is considered to be 550 mg b.i.d. (1100 mg / day). Higher doses might be explored after discussions between sponsor and investigators.
- If at least 1 subject out of 3 or 1 out of 4 in a cohort has DLTs or if at least 2 subjects report drug-related AEs (CTCAE v4.03) of Grade ≥ 2, any further dose escalation, de-escalation or cohort expansion will be decided in consultation between all investigator(s), and the sponsor (within the DSMT) after consideration of all available safety data of the previous cohorts. Any subsequent dose will be selected in order to determine the MTD.

17 Oct 2018 Version 8.0 Page: 42 of 395

Model-based dose-response analysis of the DLT rates will be performed during these interim reviews in order to guide the dose decision (see details in Section 16.4). The model-based dose selection procedure is considering data at all dose levels (not just at the last cohort). The dose predicted to yield 20% DLT rates will be reported from that model as a best candidate for the next cohort.

The final decision about the next dose will be made by the sponsor in consultation with all investigators (DSMT).

If the selected dose is larger than the last dose tested, then escalation will be pursued. If it is lower, a de-escalation step will occur.

Cohort expansion will occur when a previously tested dose is selected again for the next cohort of 3 subjects.

Expansions at any given dose up to a total of 9 subjects are allowed. In principle, the selection of a next dose level where the predicted DLT rate is close to 20% should insure that the next dose tested will remain safe.

[figure not shown]
Nevertheless, the following constraint will be added in order to protect subject safety during the adaptive dose selection decisions:

- If 2 out of 3 (or 2 out of 4), at least 4 out of 6 (or at least 5 out of 9) subjects experience DLTs at a given dose level, only lower doses will be given in all subsequent cohorts because the probability that the dose is above the MTD is very large (above 95.4%).
- The dose-escalation procedure will be stopped as soon as:
- the MTD has been defined with good precision (i.e., the coefficient of variation for the MTD is lower than or close to 40%)
- o at any time when the selected dose level for the next cohort has already been given in 9 subjects.

If the dose escalation stops, the sample size for the MTD cohort will be expanded up to a total of 20 evaluable subjects (study Part 1 / MTD expansion cohort (all comer)).

No intra-subject dose escalation is permitted. Dose interruptions and / or dose reductions may be required based on individual safety and tolerability.

**Pharmacokinetics (PK):** Single- and multiple-dose PK of BAY 1163877 will be evaluated in plasma samples collected on Cycle 1, Day -3 in the "tablet bridging cohort", and on Cycle 1, Days 1 and 15 in all subjects participating in Part 1 (all comer) and in at least 12 subjects participating in Part 2 (sqNSCLC + LAC + BC + SCCHN). In approximately 8 subjects enrolled in the MTD expansion cohorts (study Part 1 and Part 2), the effect of food on the PK of BAY 1163877 will be determined by comparing exposures on Cycle 1 Day -3 (administration after consumption of a high-fat, high-calorie breakfast) and Cycle 1 Day 1 (administration after an overnight fast of at least 8 hours), see Section 8.1. In the MTD expansion cohorts, in approximately 8 subjects with moderately impaired renal function at baseline (glomerular filtration rate [GFR] of 30 to 59 mL/min/1.73 m^2 according to the modified diet in renal disease [MDRD] abbreviated formula), serial PK blood samples will be collected on Cycle 1 Day 1 and Day 15. In all

17 Oct 2018 Version 8.0 Page: 43 of 395

subjects participating in Study Part 3/"Safety cohort", multiple dose PK of BAY 1163877 will be evaluated in plasma samples collected on Cycle 1, Day 15.34

Plasma concentration of BAY 1163877 will be measured using a validated method.

In approximately 8 subjects enrolled in MTD expansion cohorts (study Part 1 and Part 2), urine will be collected for 24 hours after dosing on Cycle 1, Day 1 (concurrently with plasma PK samples) and analyzed using validated method.

Exploratory monitoring of metabolites may also be performed in pooled plasma samples (most likely at the MTD or the therapeutic dose) and urine samples.

The time points for PK sampling and further details are provided in Section 9.4.2.1.

Safety / tolerability: Drug safety will be monitored and evaluated continuously throughout the study, including a 30-day follow up period (time window +5 days) after administration of the last dose of BAY 1163877.

Safety will be assessed by close monitoring and timely assessment of adverse events (AEs), laboratory parameters (blood tests, urinalysis), vital signs (blood pressure, heart rate), subject's medical condition (physical examination including weight), ophthalmological examination, general well-being and activities of daily life (Eastern Cooperative Oncology Group (ECOG) performance status). 35

Each subject will be regularly assessed in each cycle for potential AEs and disease related signs and symptoms. The National Cancer Institute's Common Terminology Criteria for Adverse Events, Version 4.03 (CTCAE v4.03) will be used to grade toxicities / AEs.

Subject data will be analyzed for evidence of cumulative toxicity with repeated cycles of therapy.

Women of childbearing potential must have a negative pregnancy test performed within 7 days prior to first treatment with BAY 1163877 (i.e. 1 week before Cycle 1, Day 1 or Cycle 1, Day -3, if applicable).

Cardiovascular assessment: Blood pressure (BP) and heart rate (HR) will be measured at screening, frequently on PK profile days in Cycle 1, and once at all other visits during treatment and follow up. The time points for monitoring BP and HR on the days of PK sampling and further details are provided in Section 9.4.1.1.

Assessment of immune priming (Part 3): Selected parameters of immune response will be measured in fresh tumor tissue at baseline and again between Cycle 2, Day 1 and Cycle 2, Day 21; and in peripheral blood at the following timepoints: at baseline; Cycle 1, Day 8; Cycle 2, Day 1; Cycle 2, Day 15; and on the day of the second biopsy.

Fresh tumor tissue will be used to assess immune parameters indicating a T cell response against the tumor tissue. This will be done by performing gene expression profiling

-

<sup>34 Part 3 was added by Amendment 7, see section 15.6.2.6

 Amended by Amendment 7, see section 15.6.2.6

17 Oct 2018 Version 8.0 Page: 44 of 395

(nCounter PanCancer Immune Profiling Panel) and immunohistochemistry for CD8+ T cell infiltration and PD-L1 expression on the tumor tissue. Peripheral blood will be used to collect serum to determine cytokine levels (IL-6, IFN-gamma, and other cytokines if needed). Aim of the assessment of peripheral blood is to search for changes in this easily accessible specimen that reflect the immune response in the tumor tissue.

Electrocardiogram (ECG): 12-lead ECG readings will be performed at screening, on Cycle 1, Days -3 and -2 ("tablet bridging cohort" and "food effect assessment", only), on Cycle 1, Days 1, 2, and 15, thereafter on Day 1 of each subsequent Cycle, and at the EOT visit. In all Cycles and at the EOT visit, ECG readings will be performed as single readings. The time points for ECG readings and further details are provided in Section 9.5.3.4.

Pharmacodynamic (PD) biomarkers: In an attempt to demonstrate the mechanism of action of BAY 1163877 biomarkers will be studied in tissue samples (for details see Section 9.4.4).

Biomarker analysis in tumor tissue: Biomarker analysis will be done at screening for subject stratification in the MTD expansion cohorts (Part 1: all comer; Part 2: sqNSCLC + LAC + BC + SCCHN; Part 3: sqNSCLC + LAC + BC) according to FGFR expression levels / FGFR mutation using either an archival tumor tissue specimen or fresh tumor biopsy material (see Section 7.1.1, inclusion criteria).

Analysis of phospho-extracellular signal-regulated kinase 1/2 levels, (p-ERK1/2) will be done at screening and on Cycle 2, Day 1 for all subjects of study Part 1 and Part 2 who are willing to undergo a biopsy both at screening and on Cycle 2, Day 1. Both biopsies are mandatory for "all comer" subjects included in the MTD expansion cohort of Part 1 (please refer to Section 7.1.1 for details).

Tumor response evaluation: Computed tomography (CT) or magnetic resonance imaging (MRI) of all anatomic regions involved with the disease will be performed at screening (baseline), at the end of Cycle 2 and thereafter every third cycle to assess tumor response using the Response Evaluation Criteria in Solid Tumors, Version 1.1. (RECIST v1.1)(1).

Response evaluation according to RECIST v1.1 can be done up to 5 days after CT / MR scan.

**Recommended Phase II dose (RP2D)**: The dose recommended for Phase II studies with BAY 1163877 will be determined by the investigators and the sponsor (DSMT) at the end of this study (after Part 2) after having reviewed the data from all dose levels evaluated including PK data, overall incidence and severity of AEs, cardiac safety, and amount of MTD.

<sup>36 Part 3 - Safety cohort - was added by Amendment 7, see section 15.6.2.6

<sup>37 Part 3 was added by Amendment 7, see section 15.6.2.6

38 'Study Part 1 and Part 2' added by Amendment 7 for clarification, see section 15.6.2.6

No. BAY 1163877 / 16443

17 Oct 2018 Version 8.0 Page: 45 of 395

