#### Methodology

(continued)

Without the occurrence of toxicities, dose escalation could be stopped and RP2D may be determined based on PK and/or PD results. The decision to continue treatment for an individual patient will be made by the investigator according to the criteria specified in the protocol (Section 8.4).

Cohort expansion will occur when a previously tested dose is selected again for the next cohort of 3 subjects. Expansions at any given dose up to a total of 9 subjects are allowed. In principle, the selection of a next dose level where the predicted DLT rate is close to 20% should insure that the next dose tested will remain safe. Nevertheless, the following constraint will be added in order to protect subject safety during the adaptive dose selection decisions:

- If 2 out of 3 (or 2 out of 4), at least 4 out of 6 (or at least 5 out of 9) subjects experience DLTs at a given dose level, only lower doses will be given in all subsequent cohorts because the probability that the dose is above the MTD is very large (above 95.4%).
- The dose-escalation procedure will be stopped as soon as:
  - the MTD has been defined with good precision (i.e., the coefficient of variation for the MTD is lower than or close to 40%)
  - at any time when the selected dose level for the next cohort has already been given in 9 subjects.

If the dose escalation stops, the sample size for the MTD cohort will be expanded up to a total of 20 evaluable subjects (study Part 1 / MTD expansion cohort (all comer)).

No intra-subject dose escalation is permitted. Dose interruptions and / or dose reductions may be required based on individual safety and tolerability.

17 Oct 2018 Version 8.0 Page: 16 of 395

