p.o. per os (by mouth, orally)
 PCHE plasma cholinesterase
 PD pharmacodynamic
 PD progressive disease

PD-L1 programmed death-ligand 1

p-ERK phospho-extracellular signal-regulated kinase

p-FGF phospho-fibroblast growth factor

pFRS p-FGF receptor substrate
PFS progression-free survival
PK pharmacokinetic(s)

PO4 phosphate

popPK population PK (models)
PR PR interval in ECG
PTF peak trough fluctuation

PT-INR international normalized ratio for prothrombin time

PTT partial thromboplastin time

QA quality assurance QC quality control

Qd probability of dose d being the MTD

QRSD QRS duration

QT interval in ECG

No. BAY 1163877 / 16443

al Study Protocol
7 / 16443

17 Oct 2018 Version 8.0 Page: 30 of 395

QTc QT interval corrected for heart rate

RBC red blood count

RECIST v1.1 Response Evaluation Criteria in Solid Tumors (RECIST), Version 1.1

ROS Roll-over study

RP2D recommended Phase II dose

SAE serious adverse event SAS statistical analysis system

SCCHN squamous cell carcinoma of the head and neck

sd standard deviation SD stable disease

sec second

SIS / ICF subject information sheet / informed consent form

SNR screening number

SOP standard operating procedure

SPC summary of product characteristics sqNSCLC squamous non-small cell lung cancer

SUSAR suspected unexpected serious adverse reaction  $t_{1/2}$  half-life associated with the terminal slope

Td (tolerable) probability that the DLT rate is below 0.20, Pr(p < 0.20 | d),

for a dose d

TEADR(s) treatment-emergent drug-related adverse event(s)

TEAE(s) treatment-emergent adverse event(s)

time of last plasma concentration above LLOQ

tmax time to reach maximum drug concentration in plasma after single

(first) dose

time to reach maximum drug concentration in plasma after multiple-

dose administration

TNM tumor node metastasis (classification)
TSH thyroid stimulating hormone (thyrotropin)

TTP time to progression

ULN upper limit of norm (upper limit of normal laboratory values)

USA United States of America

V apparent volume of distribution

vs. versus

Vss/F apparent volume of distribution at steady state after extravascular

administration

Vz/F apparent volume of distribution during terminal phase after oral

administration

No. BAY 1163877 / 16443

17 Oct 2018 Version 8.0 Page: 31 of 395

WBC white blood cell (count)

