#### 10.4.2 Maximum tolerated dose

Individual listings and treatment summaries of dose limiting toxicities with CTCAE v4.03 code and grade will be presented.

The incidence of subjects with DLTs during Cycle 1 will be summarized by treatment and, as possible, modeled as a function of BAY 1163877 dose using Bayesian logistic regression. The moderately-informative independent priors used during the interim analysis (see Section 16.4 for details) as well as non-informative priors will be used for this analysis in order to assess sensitivity of the estimates. Parameter estimates and model predictions will be reported with 90% credibility sets. The MTD will be computed as a derived function of model parameters as:

 $MTD = (\log(0.2/0.8) - \text{intercept}) / \text{slope}.$ 

The posterior distribution of the MTD will be summarized in tabular and graphical formats.

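### The fixed safety rule bars a dose after 2 DLTs in 4 subjects but not after 3 in 6 or 4 in 9, and its 95.4% is not reproduced for 2 in 4 under non-informative priors

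*Protocol*

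**What the plan says.** Protocol Section 6, under determination of the MTD, defines the MTD as the highest dose "such that not more than 20% of subjects experience a DLT during Cycle 1". The list of abbreviations uses the same cut: Td is the "probability that the DLT rate is below 0.20" at a given dose.

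Escalation is guided by a Bayesian logistic model and decided by the sponsor with the investigators (the drug safety monitoring team, DSMT). One fixed constraint is added to protect subjects. It reads "If 2 out of 3 (or 2 out of 4), at least 4 out of 6 (or at least 5 out of 9) subjects" with DLTs at a dose, after which only lower doses may follow, "because the probability that the dose is above the MTD is very large (above 95.4" per cent). The synopsis (Methodology) repeats it, including "at least 4 out of 6 (or at least 5 out of 9) subjects experience DLTs at a given dose level".

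Two further provisions matter. Where two or more sites take part, "the initial enrolment of 4 subjects per dose level is optional". And "Cohort expansion will occur when a previously tested dose is selected again for the next cohort of 3 subjects", up to 9 subjects at a dose. A dose can therefore be seen at 3, 6 and 9 subjects, or at 4 and 7. No count is given for 7.

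No prior is named beside the 95.4%. Section 10.4.2 says the final MTD analysis will use the moderately informative priors of Section 16.4, "as well as non-informative priors will be used for this analysis in order to assess sensitivity of the estimates".

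**The concern.** One probability is offered as the reason for all four limits, so the limits should correspond to roughly one strength of evidence. They do not appear to. Two DLTs in 4 and three in 6 are both 50%, and the larger sample is firmer evidence of a rate above 20%. Yet the smaller one bars the dose and the larger one does not.

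This is the only hard limit in a first-in-human escalation. Where it is silent, protection rests on the model and on judgement. A dose with 3/6 or 4/9 DLTs is not excluded by rule. It could be repeated up to 9 subjects and, if taken as the MTD, expanded to 20.

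**Working it through.** **Inputs.** DLT rate defining the MTD: 0.20 (Section 6). Limits: 2/3, 2/4, at least 4/6, at least 5/9 (Section 6). Stated probability: above 95.4%. The prior behind that figure is not in the text available, so flat Beta(1,1) and Jeffreys Beta(0.5,0.5) are assumed.

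**How the counts are read.** They are cumulative per dose. If 2 out of 3 applied to each new cohort of 3, the limits at 6 and 9 would be redundant, because 4/6 or 5/9 cannot occur without some cohort having at least 2 DLTs.

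**Step 1: the stated figure.** With x DLTs in n subjects and prior Beta(a,a), the posterior is Beta(x+a, n−x+a), and the quantity wanted is P(p > 0.20). Under the flat prior this equals P(Bin(n+1, 0.2) ≤ x). For 2/4: 0.32768 + 0.4096 + 0.2048 = 0.94208.

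| Count | In the rule? | Flat | Jeffreys |
|---|---|---|---|
| 2/3 | yes | 97.3% | 96.6% |
| 2/4 | yes | 94.2% | 92.3% |
| 4/6 | yes | 99.5% | 99.4% |
| 5/9 | yes | 99.4% | 99.2% |
| 3/6 | no | 96.7% | 95.6% |
| 4/9 | no | 96.7% | 95.7% |
| 4/7 | no | 99.0% | 98.7% |
| 3/7 | no | 94.4% | 92.6% |

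Three of the four listed counts reproduce; 2/4 falls short by 1.2 points (flat) or 3.1 points (Jeffreys). The unlisted 3/6 and 4/9 pass, narrowly under Jeffreys.

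**Step 2: does the ordering depend on the prior?** Going from 2/4 to 3/6 multiplies the likelihood by p(1−p). This is below 0.16 for every rate under 20% and above 0.16 for every rate between 20% and 80%. So 3/6 is the stronger evidence unless the prior puts real weight above 80%. For 4/9 the factor is p²(1−p)³, which exceeds its value at 20% (0.0205) up to a rate of about 62%.

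On a grid of 20,000 Beta priors (a 0.05–5, b 0.05–10), 3/6 exceeds 2/4 under all of them. 4/9 falls below 2/4 under 890, all strongly favouring toxicity. No prior on the grid puts 2/4 above 95.4% while leaving 3/6 or 4/9 at or below it.

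Which counts pass does depend on the prior. Near the Beta(0,0) limit, 2/3 is 96.0%, 2/4 is 89.6%, 3/6 is 94.2% and 4/9 is 94.4%. The order is unchanged.

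**Step 3: effect on barring.** Assume cohorts of 3+3+3, the dose repeated each time, and the model and DSMT ignored. At a true rate of 50%, in units of 1/512:

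- Listed rule: 256 at n=3, 24 at n=6, 52 at n=9; total 332, or 64.8%.
- With at least 3/6: 256 + 104 + 12 = 372, or 72.7%.
- With at least 3/6 and at least 4/9: 256 + 104 + 54 = 414, or 80.9%.

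| True DLT rate | Listed | 3/6 and 4/9 added |
|---|---|---|
| 20% | 11.3% | 17.2% |
| 30% | 25.5% | 38.5% |
| 40% | 44.4% | 61.7% |
| 50% | 64.8% | 80.9% |

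**Step 4: cohorts of 4+3.** With 2/4 alone, barring is 18.1% at a true 20% and 68.8% at a true 50%. Adding at least 4/7 gives 18.4% and 71.9%. Adding at least 3/7 instead gives 22.7% and 82.0%.

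**The case against.** The strongest reply is that the benchmark is not the protocol's model. The MTD comes from a two-parameter logistic regression using data at all doses, with a prior set out in Section 16.4. Section 10.4.2 offers non-informative priors only as a sensitivity check on the final analysis. This stands: 95.4% may be right under that prior, so a reader should not conclude that it is an arithmetic error.

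A reader might also infer that any prior supporting 95.4% at 2/4 must assume the dose is very probably too toxic beforehand. Single-dose Beta priors point that way, with at least about 85% prior probability of a rate above 20%. The floor does not carry over to logistic priors: under assumed priors of that form, all four counts passed with prior probability as low as 72%. That inference should not be drawn.

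Next, the text says the listed outcomes have high probability, not that every such outcome is listed. That is also true; the omission is a gap in the rule, not a false statement. Nor are subjects unprotected at 3/6 or 4/9. Any cohort with a DLT goes to the DSMT, and the model aims at 20% using all data.

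The benefit also needs qualifying. Of the 16.0-point gain at a true 50%, 8.2 points arise at 9 subjects, where the cap already prevents another escalation cohort. There the change mainly stops such a dose being named the MTD and expanded.

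Finally, this version reads as though escalation is over, since it reports biopsy findings from the study and doses Part 3 at the Part 1 MTD. That is an inference, and the rule still stands in the current text, but it limits the practical effect.

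None of this answers the mismatch between 2/4 and 3/6.

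**Conclusion.** The point holds as an incoherence in the fixed rule: it acts at 2/4 and is silent at 3/6 and 4/9, which under both standard non-informative priors are stronger evidence that the rate exceeds 20%. The stated 95.4% is not reproduced for 2/4 under those priors, while the two unlisted counts meet it.

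The shortfall at 2/4 is small, errs on the cautious side, and arises only with the optional cohort of 4. The barring probabilities are upper bounds, since they assume repetition to 9 subjects with no model or DSMT intervention. Severity is modest, because those two remain the primary control. It is still worth correcting, because this is the rule meant to hold when they do not.

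**What to change.** In Section 6 and the synopsis:

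- Apply the 95.4% cut consistently: bar at 2/3 or more, at least 3/6, at least 4/9 and, for cohorts of 4 then 3, at least 4/7. 3/7 falls below the cut.
- Keep 2/4 as an explicitly cautious trigger with its own figure: about 94% (flat) or 92% (Jeffreys), or the Section 16.4 value if that is the source. Do not relax it to 3/4, which would cut first-cohort barring of a true 50% dose from 68.8% to 31.3%.
- Do not lower the general figure to 94%. At that level 3/7 (94.4% flat) would have to bar as well, adding 4.6 points of barring at a true 20% (18.1% to 22.7%).
- Name the prior beside the figure. If Section 16.4 does give above 95.4% at 2/4, cite it and still add 3/6 and 4/9.

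The cost is one recalculation and edits in two places, with no extra subjects or data. The price in performance is more frequent barring of a dose exactly at 20%: from 11.3% to at most 17.2% with cohorts of 3, and 0.3 points from the 4/7 limit.
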